7.3.2.2 Secondary Efficacy Analyses

The analysis of the continuous secondary efficacy variables at Week 4 Follow-up Visit post IP removal of Treatment 1 may be analyzed similarly as for the primary efficacy variable of average daily bladder pain NRS, as described in Section 7.3.2.1 Primary Efficacy Analyses. However, no imputation method will be applied.

7.3.3 Safety Analyses

Safety data will be analyzed using safety population.

Safety assessments will be reported by treatment group and will include:

- adverse events
- clinical laboratory results
- urinalysis
- urine culture and sensitivity
- vital signs
- PVR volumes

Adverse events will be mapped to a Medical Dictionary for Regulatory Activities (MedDRA) preferred term and system organ classification (SOC) using MedDRA.

The following analyses will be performed:

- 1. Summaries by treatment group and overall for Treatment 1
- 2. Overall summaries for all patients who received Treatment 2
- 3. Summaries for patients who participated in both Treatment 1 and Treatment 2 by treatment group and overall

Safety Analyses

- 1. Occurrence of adverse events using MedDRA preferred term, primary SOC, and severity. If a patient experiences multiple events that map to a single preferred term, the greatest severity and strongest investigator assessment of relation to the IP will be assigned to the primary SOC and preferred term for the appropriate summaries.
- 2. All adverse events for individual patients showing both verbatim, preferred term, and primary SOC
- 3. Serious adverse events and adverse events related to the IP, the device constituent alone (silicone device/nitinol wire/elastomer components), and the drug (lidocaine) constituent alone; overall summary by preferred term, primary SOC, and severity
- 4. Serious adverse events and adverse events related to the procedure (cystoscopy, IP insertion procedure or the IP removal procedure); overall summary and summary by preferred term, primary SOC, and severity
- 5. Descriptive summaries of clinical laboratory results (see Section 6.5.5 for detailed listings of the specific laboratory analytes)
- 6. Clinical laboratory abnormality shifts from baseline
- 7. Descriptive summaries of vital signs including systolic and diastolic blood pressure, heart rate, respiratory rate, and body temperature
- 8. Descriptive summaries of PVR volume measurements

9. Prior and concomitant medication (coded using World Health Organization [WHO]-Drug Dictionary)

7.4 Pharmacokinetic Analysis

Blood and urine concentration data generated for lidocaine and 2,6-xylidine will be used for pharmacokinetic assessment in plasma and urine. A contributing report will be provided for inclusion in the final report.

7.5 Missing Data

Every effort will be made to obtain required data at each scheduled evaluation from all patients who have been enrolled. Missing data will only be imputed for the analysis of the primary efficacy variable. Any deviations to the SAP made after database lock will be documented in the final Clinical Study Report.

7.6 Subgroup Analyses

There is no pre-planned subgroup analysis. Any subgroup analysis will be done in an ad hoc manner after data base lock.

7.7 Sample Size Calculation

Based on the assumption that 5% of the randomized patients will not be evaluable for the primary analysis, approximately 76 patients will be enrolled into the study to ensure 72 evaluable patients overall. At a randomization ratio of 2:1:1, 72 evaluable patients will ensure that there will be about 36 patients in the LiRIS 400 mg/LiRIS 400 mg group, 18 patients in the LiRIS Placebo/LiRIS 400 mg group, and 18 patients in the LiRIS Placebo group.

A sample size of 36 patients in the LiRIS 400 mg/LiRIS 400 mg group versus 18 patients in the LiRIS Placebo/LiRIS Placebo group will have 76% power to detect a difference of 1.152 in mean daily average bladder Pain NRS, assuming that the common standard deviation is 1.67 using a 1-sided 2-group t-test with a 0.05 significance level.

The standard deviation assumption is

based on the results of the TAR-100-105 open-label study, where the standard deviation is the Week 4 Follow-up raw average daily NRS.

7.8 Interim Analyses

After approximately 50% of patients enrolled complete the Treatment 1 Week 4 Follow-up visit, an estimate of the standard deviation for the primary variable may be derived based on the blinded data review. If such an assessment results in a drastically different standard deviation than what is assumed for the derivation of the sample size in the protocol, the study sample size may be decreased or increased, depending on the result of the sample size derivation.

Futhermore, an interim analysis may be performed after at least 25 patients have been enrolled. If such an interim analysis is to be performed, details of the interim analysis and procedures to maintain blinding of treatment groups and confidentiality of results will be presented in the SAP.

8. Study Visit Schedule and Procedures

Please see Table 1 for the schedule of visits and procedures, Figure 1 for the visit flow chart, and Section 6.5 for detailed information on study procedures, tests, equipment, and techniques.

8.1 Patient Entry Procedures

8.1.1 Overview of Entry Procedures

Prospective patients as defined by the criteria in Sections 4.3 and 4.4 (inclusion/exclusion criteria) will be considered for entry into this study.

8.1.2 Informed Consent and Patient Privacy

The study will be discussed with the patient and a patient wishing to participate must give informed consent prior to any study-related procedures or change in treatment. The patient must also give authorization (US only) and other written documentation in accordance with the relevant country and local privacy requirements (where applicable) prior to any study-related procedures or change in treatment.

Each patient that provides informed consent and/or assent will be assigned a patient number by IVRS/IWRS that will be used on patient documentation throughout the study.

8.2 **Procedures for Final Study Entry**

Final study eligibility will be determined at the Randomization/Day 0 visit to confirm that patient baseline pain assessment and bladder diary record support protocol requirement for IC with HL. In addition, the investigator should confirm that the "day of treatment criteria" have been fulfilled (Section 5.8.1). Patients should continue to meet other inclusion and exclusion criteria as specified in Sections 4.3 and 4.4 of the protocol.

A patient is considered to have entered the study when they are randomized to treatment.

See Section 5.5 for the method for assignment to treatment groups/randomization.

8.3 Visits and Associated Procedures

For a summary of the procedures to be performed, see Table 1 (Schedule of Visits and Procedures). A description of individual procedures is provided in Section 6.5. The total number of clinic visits and study duration for each patient will depend on whether patients request and qualify for retreatment. Evaluations should be performed by the same evaluator throughout the study whenever possible. During the study, every effort should be made to perform the study procedures as indicated in Table 1.

8.4 Instructions for the Patients

Patients will be instructed on the following:

- pain assessment tool and bladder diary completion (Sections 6.5.12 and 6.5.13)
- complete and bring diaries (electronic and paper) to the study site at each scheduled clinic study visit
- contact the study site (or have a family member or friend contact the study site) to report any hospitalizations
- maintain the dose of any concurrent medication. If there are changes to medications, dosage, or frequency, the changes should be reported to the investigator at the next study visit.
- report all usage of rescue medications to the investigator at the next study visit (see Section 4.5.3)

- call the study site if they are experiencing any difficulties following study procedures
- call the study site as soon as possible in order to reschedule, if the patient cannot make their next scheduled study visit

8.5 Unscheduled Visits

Unscheduled visits can be performed if safety concerns arise and at the discretion of the investigator. Additional examinations may be performed as necessary to ensure the safety and wellbeing of patients during the study. eCRFs will be completed for each unscheduled visit.

8.6 Compliance With Protocol

Participating patients should be able to adhere to the diary completion and testing parameters as described in this protocol.

Data will be recorded on the appropriate eCRF supported by appropriate source documentation. At each visit, patients should be asked if any concomitant medications had been used, if they had undergone any concurrent procedures (nonstudy procedures), and their compliance with the protocol since the previous visit.

8.7 Early Discontinuation of Patients

Patients may voluntarily withdraw from the study at any time. If the withdrawal occurs during the treatment period in which the IP is in the patient's bladder, the patient should contact the study site to schedule a visit for IP removal. If a patient exits the study prior to completion, all Exit Visit assessments should be performed at the time of exit.

Notification of early patient discontinuation from the study and the reason for discontinuation will be made to Allergan and will be clearly documented on the appropriate eCRF.

8.8 Withdrawal Criteria

Patients have the right to withdraw from the study at any time and for any reason without prejudice to his or her future medical care by the physician or the institution. The investigator and Allergan also have the right to withdraw a patient from the study at any time for any reason.

Patients should be discontinued from the study if any of the following criteria are met:

- patient develops (or has an exacerbation of) any medical condition that, in the opinion of the investigator, would put the patient at an unacceptable medical risk or compromises the patient's ability to participate in the study
- patient becomes pregnant (see Section 4.5.1.1 for Definition of Females of Childbearing Potential and Acceptable Contraceptive Methods)
- patient is unwilling or unable to continue to comply with study procedures

Where possible, the decision to withdraw a patient from study treatment or the study should be discussed with Allergan.

8.9 Study Termination

The study may be stopped at his/her study site at any time by the site investigator. Allergan may stop the study (and/or the study site) for any reason with appropriate notification.

9. Adverse Events

Adverse events occurring during the study will be recorded on an adverse event eCRF. If adverse events occur, the first concern will be the safety of the study participants.

9.1 Definitions

9.1.1 Adverse Event

An adverse event is any untoward medical occurrence in a patient or clinical investigation subject administered a pharmaceutical product and that does not necessarily have a causal relationship with this treatment. An adverse event can therefore be any unfavorable and unintended sign (including an abnormal laboratory finding), symptom, or disease temporally associated with the use of a medicinal (investigational) product, whether or not related to the medicinal (investigational) product. In addition, during the Screening period, adverse events will be assessed regardless of the administration of a pharmaceutical product.

Note: Adverse events must be collected once informed consent has been obtained, regardless of whether or not the patient has been administered study IP.

Progression of treatment indication including new or worsening of anticipated clinical signs or symptoms, which are collected as clinical efficacy variables and assessed as unequivocally associated with the disease progression and/or lack of efficacy, should NOT be reported as

adverse events unless the disease progression is greater than anticipated in the natural course of the disease.

Adverse events will be assessed, documented, and recorded in the eCRF throughout the study (ie, after informed consent has been obtained). At each visit, the investigator will begin by querying for adverse events by asking each patient a general, non-directed question such as "How have you been feeling since the last visit?" Directed questioning and examination will then be done as appropriate. All reported adverse events will be documented on the appropriate eCRF.

9.1.2 Definition of Adverse Event of Urinary Tract Infection

An adverse event of UTI is defined as a UTI based on the investigator's decision to initiate antibiotic treatment (due to results from urine analysis + urine culture or patient's symptoms with appropriate findings in the urine analysis and culture in the investigator's opinion).

Note: If urinalysis/culture results are reported which, in the opinion of the investigator, are considered clinically relevant but do not fulfill the above definition of a UTI as no antibiotic treatment is initiated by the investigator, the findings should be recorded as adverse events (eg, bacteriuria, leukocyturia).

9.1.3 Serious Adverse Event

A serious adverse event is any adverse event occurring at any dose that results in any of the following outcomes: death, a life-threatening adverse event, inpatient hospitalization or prolongation of existing hospitalization, a persistent or significant disability/incapacity, or a congenital anomaly/birth defect. Important medical events that may not result in death, be life-threatening, or require hospitalization may be considered a serious adverse event when, based upon appropriate medical judgment, they may jeopardize the patient or subject and may require medical or surgical intervention to prevent one of the outcomes listed in this definition. (See Section 9.3 for procedures for reporting a serious adverse event.)

Allergan considers all cancer adverse events as serious adverse events. In addition, Allergan considers any abortion (spontaneous or nonspontaneous) as a serious adverse event.

Pre-planned surgeries or procedures for pre-existing, known medical conditions for which a patient requires hospitalization is not reportable as a serious adverse event.

Any pre-planned surgery or procedure should be clearly documented in the site source documents by the medically qualified investigator at the time of the patient's entry into the

study. If it has not been documented at the time of the patient's entry into the study, then it should be documented as a serious adverse event and reported to Allergan.

9.1.4 Severity

A clinical determination will be made of the intensity of an adverse event. The severity assessment for a clinical adverse event must be completed using the following definitions as guidelines:

Mild	Awareness of sign or symptom, but easily tolerated.
Moderate	Discomfort enough to cause interference with usual activity.
Severe	Incapacitating with inability to work or do usual activity.
Not applicable	In some cases, an adverse event may be an "all or nothing" finding which cannot be graded.

9.1.5 Relationship to Study Investigational Product or Study Procedure

A determination will be made of the relationship (if any) between an adverse event and the study IP or study procedure, as applicable. A causal relationship is present if a determination is made that there is a reasonable possibility that the adverse event may have been caused by the IP or study procedure.

9.2 Procedures for Reporting Adverse Events

Any adverse event must be recorded on the appropriate eCRF.

All adverse events that are IP-related and unexpected (not listed as treatment-related in the current Investigator's Brochure) must be reported to the governing Institutional Review Board/Independent Ethics Committee (IRB/IEC) as required by the IRB/IEC, local regulations, and the governing health authorities. Any adverse event that is marked "ongoing" at the Exit Visit must be followed-up as appropriate.

9.3 **Procedures for Reporting a Serious Adverse Event**

Any serious adverse event occurring during the study period (beginning with informed consent) and for at least 28 days after the last dose of study IP must be immediately reported but no later than 24 hours after learning of a serious adverse event. Serious adverse events

must be reported to Allergan (or agent of Allergan) as listed on the Allergan Study Contacts Sheet and recorded on the serious adverse event Form. All patients with a serious adverse event must be followed up and the outcomes reported. The investigator must supply Allergan and the IRB/IEC with any additional requested information (eg, autopsy reports and discharge summaries).

In the event of a serious adverse event, the investigator must:

- 1. Notify Allergan immediately by fax or email using the serious adverse event form (contact details can be found on page 1 of the serious adverse event form); phone numbers and relevant Allergan personnel contacts are also on the front page of protocol.
- 2. Obtain and maintain in his/her files all pertinent medical records, information, and medical judgments from colleagues who assisted in the treatment and follow-up of the patient.
- 3. Provide Allergan with a complete, written description of the adverse event(s) on the serious adverse event form describing the event chronologically, including any treatment given (eg, medications administered, procedures performed) for the adverse event(s). Summarize relevant clinical information about the event: signs, symptoms, diagnosis, clinical course and relevant clinical laboratory tests, etc. Include any additional or alternative explanation(s) for the causality which includes a statement as to whether the event was or was not related to the use of the investigational IP.
- 4. Promptly inform the governing IRB/IEC of the serious adverse event as required by the IRB/IEC, local regulations, and the governing health authorities.

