1.4 Clinical Studies

A series of phase 1 and phase 2 studies have been conducted in humans including healthy female adults, IC/BPS and IC with HL female patients to assess the safety and efficacy of TARIS Placebo and LiRIS (200 mg, 400 mg, and 650 mg).

The TARIS Placebo system was tested in a phase 1, single-blind, randomized, placebocontrolled (via sham procedure), parallel group study (Study TAR-100-101), to evaluate the positional stability and patient tolerance of the system within the bladder over 14 days, evaluating design implications of the insertion and removal procedures. A total of 10 healthy female volunteers were enrolled in the study; 7 patients underwent insertion and retrieval of the TARIS Placebo system and 3 patients had the sham procedure (cystoscopy only). The results of this study showed that the TARIS Placebo system was generally well tolerated in healthy female volunteers as adverse events such as haematuria, dysuria, urethral pain, and abdominal pain were similar to those seen with the sham procedure.

The LiRIS 400 mg was tested in a phase 2a multicenter, randomized, double-blinded, placebo-controlled study (Study TAR-100-201) to evaluate safety, tolerability, and efficacy in female patients with IC/BPS in North America. The study compared LiRIS 400 mg to LiRIS Placebo over a 14-day treatment period and 4-week follow-up period. Data collected from the 104 enrolled patients showed trends of improvement with LiRIS 400 mg in sub-populations of IC/BPS patients with high bladder pain at baseline (7 or greater on 0 to 10 cm visual analogue scale [VAS]) and in patients 40 years of age or older at time of enrollment. Overall, adverse events seen in 10% or more of enrolled patients were bladder pain, dysuria, haematuria, and urinary tract infections (UTIs). The majority of adverse events were mild or moderate in intensity. There was no meaningful difference in the incidence of these events between the LiRIS 400 mg and LiRIS Placebo groups.

A phase 1b pilot safety, tolerability and preliminary efficacy, multicenter, open-label, ascending dose study (Study TAR-100-103) of LiRIS was conducted in a mixed female patient population with IC/BPS and IC with HL. The study enrolled 16 patients in 2 cohorts

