5.6 Treatment Regimen and Dosing

5.6.1 Treatment 1

Eligible patients will be randomized on Randomization/Day 0 to receive Treatment 1, LiRIS 400 mg/LiRIS 400 mg; LiRIS Placebo/LiRIS Placebo or LiRIS Placebo/LiRIS 400 mg (Section 5.4). Patients will have the Treatment 1, 1st IP inserted on Randomization/Day 0 and removed on Day 14. On the same day, following the 1st IP removal, the 2nd IP (LiRIS 400 mg or LiRIS Placebo) will be inserted and subsequently removed on Day 28. Patients will be followed for 20 weeks post IP removal for additional safety and efficacy assessments. In the event that a patient does not receive Treatment 2, they will exit the study at Treatment 1 Week 20 Follow-up Visit.

5.6.2 Treatment 2

All patients will receive LiRIS 400 mg for their second treatment. Patients may request, qualify, and receive Treatment 2 IP from Week 4 Follow-up until Week 20 of Treatment 1. In the event that the Treatment 2 IP cannot be inserted on the day of qualification, Treatment 2 may be rescheduled within 14 days of qualification. The LiRIS will be inserted on Treatment 2/Day 0, and will be removed on Day 14. Patients will be followed for 4 weeks post-removal and will be exited from the study.

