6.5.18 Concomitant Medications and Concurrent Procedures

Patients will be instructed to capture all pain medication (stable dose and rescue medications) taken for IC pain during the study on the electronic diary which will capture what medication was taken and when (date and time). Site staff will review the pain medication electronic

diary and capture missing or incomplete pain medication information as required. Site staff will also query patients regarding use of any other medications while participating in the study.

Concomitant medication information, including name of medication, dose, route, date will be collected at each study clinic and phone visit starting at the time of Screening and ending at the patient Exit Visit (either at completion of follow-up to Treatment 1 or Treatment 2, as applicable).

All concomitant medications and concurrent procedures must be recorded in the eCRF with all specific details associated with each use of the medication/procedure.

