12.0 SAFETY ANALYSES

The safety analysis will be performed using the Safety Population. The safety parameters will include adverse events (AEs) and clinical laboratory and vital signs parameters, physical and pelvic assessments. For each clinical laboratory and vital sign parameters, the last non-missing safety assessment before the first Treatment 1 IP insertion will be used as the baseline for all analyses of that safety parameter. Continuous variables will be summarized by number of patients and mean, SD, median, minimum, and maximum values. Categorical variables will be summarized by number of patients.

All safety analyses will be performed using the safety population. For such analyses, subjects will be analyzed according to actual treatment received at the study treatment visit (i.e., "as treated" rather than "as randomized").

The following safety analyses will be performed unless otherwise mentioned:

- Summaries by treatment group and overall for the Treatment 1 period
- Summaries for patients who participated in both the Treatment 1 period and Treatment 2 period by treatment group and overall patient population. In this analysis, the treatment groups will be the safety treatment groups.

12.1 **ADVERSE EVENTS**

Adverse events will be coded by system organ class and preferred term using the *Medical Dictionary for Regulatory Activities*, version 18.1 or newer.

An AE will be considered a treatment-emergent adverse event (TEAE) if it was present after the first dose of study treatment or was present before the date of the first dose of study treatment and increased in severity after the first dose of study treatment or became serious after the first dose of study treatment. If more than 1 AE was reported before the first dose of study treatment and coded to the same preferred term, the AE with the greatest severity will be used for comparison with the AEs occurring during the study period.

Analysis of the incidence of TEAEs will be performed for the Treatment 1 Period using the Safety population. For the cohort of safety patients that received Treatment 2 IP, the incidence of TEAEs will be summarized over the Treatment 2 Period and over the entire study period (Treatment 1 and 2 period). The following rules will be used to count TEAEs at each treatment period.

- For the analyses of TEAEs by treatment period, an event will be counted once in the particular period if the onset of this event begins during that corresponding period.

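### Patients who exit at or soon after IP removal have no stated collection of new non-serious AEs after exit, and the start of the 28-day SAE window is undefined for an indwelling device

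*Protocol*

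**What the plan says.** **Non-serious events.** Protocol Section 9.1.1 has AEs recorded from consent for as long as the patient is in the study. Section 6.5.18 has concomitant medication collected at each clinic and phone visit, "ending at the patient Exit Visit". Section 9.2 adds that an AE still ongoing at exit is to be followed.

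**Leaving early.** Section 8.7 states: "If the withdrawal occurs during the treatment period in which the IP is in the patient's bladder, the patient should contact the study site" to arrange removal. It continues: "If a patient exits the study prior to completion, all Exit Visit assessments should be performed at the time of exit". No later contact is mentioned there.

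**Serious events.** Section 9.3 covers the study period from consent and, in addition, runs "for at least 28 days after the last dose of study IP".

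**Patients who complete.** Section 5.6.1 follows Treatment 1 patients for 20 weeks after removal. For Treatment 2, Section 5.6.2 says: "Patients will be followed for 4 weeks post-removal and will be exited from the study".

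**SAP.** Section 12.1 treats an event as treatment-emergent "if it was present after the first dose of study treatment". The same section counts lidocaine events of special interest from insertion to the day after removal.

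**The concern.** The days just after removal are when events caused by the removal procedure, or by a poorly tolerated device, would be expected to appear, and the documents treat them that way. SAP Section 17.2.1 drops the removal day and the following day from the weekly pain means because of procedure pain. Protocol Section 7.3.3 plans a summary of AEs related to the removal procedure. In the earlier randomised study of LiRIS 400 mg (Section 1.4), "adverse events seen in 10% or more of enrolled patients were bladder pain, dysuria, haematuria, and urinary tract infections".

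A patient who withdraws and exits on the day of removal contributes almost nothing to that picture. A urinary tract infection that starts three days later, for example, is a new event, so the rule on following ongoing AEs does not catch it. Early leavers may include those who tolerated the device worst, so this is a poor group in which to stop asking.

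The SAE clause adds a second uncertainty. For a tablet, the last dose is a date. For a device that releases drug over 14 days, it could be the insertion or the end of exposure, and sites could apply either.

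**Working it through.** The 28 days is a stated rule, so there is no figure of the plan's own to reproduce for this point. The check is day arithmetic plus a reading of the text.

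**Inputs**
- SAE minimum: 28 days from the last dose (Protocol 9.3).
- Scheduled dwell time of each IP: 14 days (Protocol 5.6).
- Follow-up after removal in completers: 20 weeks = 140 days (Treatment 1 only) or 4 weeks = 28 days (Treatment 2).
- Dropout allowance: 5% of 76 enrolled (Protocol 4.1).
- Planned arm sizes: 38, 19 and 19 (Protocol 3).

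**1. New non-serious AEs.** If a patient exits k days after removal, stated collection after removal lasts k days. With same-day exit, k = 0. The shortest follow-up in completers is 28 days, so the difference is 28 − 0 = 28 days.

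**2. SAEs, for a patient who exits on the removal day.** If the last dose is the insertion, required days after removal = 28 − dwell time. If it is the removal, the answer is 28 whatever the dwell time.

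| Dwell time of last IP (days) | SAE days after removal, dose = insertion | SAE days after removal, dose = removal |
|---|---|---|
| 1 | 27 | 28 |
| 3 | 25 | 28 |
| 7 | 21 | 28 |
| 10 | 18 | 28 |
| 14 | 14 | 28 |

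Within the 14-day schedule the two readings differ by at most 14 days, and by less when removal is early.

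**3. Completers.** They are in the study for 28 or 140 days after removal, so SAEs are covered for at least 28 days on either reading. There is no gap.

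**4. Which reading is meant.** SAP 12.1 starts treatment emergence at the first dose, and SAP 9.0 starts concomitant medication at the first insertion, so first dose and insertion coincide. That does not settle the last dose, because exposure begins at insertion on either reading. SAP 17.4 marks a missing last-dose date as not applicable, yet SAP 17.8.2 uses the last dose to impute medication stop dates. Neither document defines the term.

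**5. Lidocaine-event window.** The SAP 12.1 window closes on the day after removal. Exit on the removal day ends stated non-serious collection one day before that.

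**6. Scale.** 5% × 76 = 3.8, so about 4 patients if every patient in the allowance left on the removal day. If, as an assumption, 10% to 40% of them had a new AE after removal, 4 × 0.10 = 0.4 to 4 × 0.40 = 1.6 patients' events would go unrecorded. As a share of all patients that is 5% × 10% = 0.5 to 5% × 40% = 2.0 percentage points. One patient weighs 1/38 = 2.6 points in the larger arm and 1/19 = 5.3 points in a smaller one.

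**The case against.** **Premature removal is not exit.** Protocol 5.6.3 lists reasons for removing the IP, including the patient's request, and requires only removal. SAP 11.1 provides for patients with a single IP and counts their Week 4 Follow-up from that removal. A patient who tolerates the device badly can therefore stay under full AE collection. Section 4.5.1.1 has pregnant patients exit only after safety follow-up. This stands, and it confines the gap to patients who actually leave the study at or soon after removal.

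**The schedule cannot be read.** The visit tables in both documents are missing from the text available, and Section 6.5.18 mentions phone visits, so a contact after exit listed there cannot be ruled out. This is a fair limit on the finding. The readable text still makes exit the end of collection: Section 6.5.18 for medication, Section 6.5.12 for pain scores (the day before exit), and Section 8.7 with no later contact. If the schedule does contain one, Sections 8.7 and 9.3 should refer to it.

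**The SAE clause may be adequate.** The 28 days is a minimum added to the whole study period. If the last dose means the end of exposure, nothing is short. This stands.

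**The scale is soft.** The 5% is an allowance for dropout and for patients not evaluable for the primary analysis, not a rate of exit on the removal day. The 10% figure in Section 1.4 describes events over a whole earlier study, not onset after removal. This also stands, so the counts above are illustrative and lean high.

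**Conclusion.** The gap in non-serious AE collection holds on the readable text. A patient who exits on the removal day has 0 stated days of collection for new non-serious events after removal, against at least 28 in any completer, and leaves before the SAP's own lidocaine window has closed. The SAE clause is an undefined term: 14 to 27 days of cover after removal on one reading, 28 on the other.

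Two stronger conclusions might be inferred, and the documents support neither. One is that SAEs are being lost. That follows only if the last dose is the insertion, which the documents do not say. The other is that the comparison between arms is distorted. That needs early leaving to differ by arm, for which there is no evidence here. In the earlier study the common events showed no meaningful difference between active and placebo (Section 1.4).

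The effect is small: at most about 4 of 76 patients under the plan's own allowance, with the true number not given. It concerns safety data only. Efficacy, sample size and power are untouched. The change is worth making because it is cheap and improves data in a group likely to include poor tolerators.

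**What to change.** 1. **Protocol 9.3:** count the 28 days from removal or voiding of the last IP. If no removal is documented, continue until removal is confirmed and for 28 days after that.
2. **Protocol 8.7:** for any patient who exits less than 28 days after that date, add one safety contact at 28 days, for example by phone, to collect all AEs and concomitant medication unless she refuses contact.
3. **SAP 12.1 and 17.2:** tabulate these events in the treatment period of onset, as SAP 12.1 already does. Because SAP 17.2 ends each period at study exit, add that for early leavers the current period extends to the end of the 28-day window. Without this, an event after exit belongs to no period.

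The cost is a few lines of text and one added contact for a few patients. The contact is new: Section 9.3 sets a 24-hour reporting limit once a site learns of an SAE but schedules no call. Completers need nothing extra, because their follow-up already reaches 28 days after removal.
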